Template 57 Number and percentage of subjects with at least one RSV-RTI progressing to RSV-LRTI, RSV-severe LRTI, RSV-very severe LRTI and RSV hospitalization from vaccination dose 1 up to end of <first, second> RSV season for pooled RSV 1D, RSV 2D and Comparator/Placebo groups <ES, Exposed Set with negative RSV exposure status>	97

LIST OF ABBREVIATIONS

[figure not shown]
AE	Adverse event
AESI	Adverse Events of Special Interest
ChAd155-RSV	Investigational recombinant chimpanzee adenovirus Type 155-vectored RSV vaccine
CI	Confidence Interval
ERD	Enhanced Respiratory Disease
ES	Exposed Set
GMC	Geometric mean antibody concentration
GMT	Geometric mean antibody titre
GSK	GlaxoSmithKline
LL	Lower Limit of the confidence interval
LLOQ	Lower Limit of Quantification
LRTI	Lower respiratory tract infection
MedDRA	Medical Dictionary for Regulatory Activities
NA	Not Applicable
PD	Protocol Deviation
PPS	Per-Protocol Set
RR	Relative Risk
RSV	Respiratory Syncytial Virus
RTI	Respiratory Tract Infection
SAE	Serious adverse event
SAP	Statistical Analysis Plan
SD	Standard Deviation
SDTM	Study Data Tabulation Model
SPM	Study Procedure Manual
SR	Study Report
TFL	Tables Figures and Listings
ToC	Table of Content
UL	Upper Limit of the confidence interval
ULOQ	Upper Limit of Quantification

1. DOCUMENT HISTORY

Date	Description	Protocol Version
27 MAR 2019	Final	Amendment 3: 21 MAR 2019

2. STUDY DESIGN

Figure 1 Study design

D: Day; **FU:** follow-up; **IDMC:** Independent Data Monitoring Committee; **iSRC:** internal Safety Review Committee; **RSV:** respiratory syncytial virus; **RTI:** respiratory tract infection; **SE:** solicited events; **V:** Visit **1D:** 1 Dose (1.5×10^{10} vp/dose); **2D:** 2 Dose (5×10^{10} vp/dose); **FB:** Formulation buffer S9b.

* Vaccine Dose 1 at Day 1 will be administered before the first RSV season (refer to Section 5.1 of the protocol for definition of RSV season).

† Visit 2 (Day 8), Visit 4 (Day 38), and Visit 8 (no blood sampling for immune response and no vaccine administration) may take place in the subject's home or at the investigators clinical facility as appropriate to the circumstances in the judgment of the investigator. For authorized sites only, Visit 5 (Day 61) and Visit 7 (both with blood sampling) may also take place in the subject's home or at the investigators clinical facility as appropriate to the circumstances in the judgment of the investigator.

‡ In countries where Mencevo or Placebo is used as a comparator, no administration will be performed at Day 121 and therefore in those countries there will be no Visit 6 and it will be administered at the end of the first RSV season at Visit 7 (refer to Table 2 and Table 7 of the protocol).

a Surveillance for RSV-RTI comprises monthly nasal swab collected to detect asymptomatic RSV infections during RSV season and active and passive surveillance contacts for RSV symptomatic RTI. Of note the swab may be omitted if a nasal swab has been taken at a symptomatic visit in the same month (see Section 9.2 of the protocol). Data about RSV-RTI incidence will be reviewed monthly by an IDMC.

b An iSRC will review all accumulating safety data monthly until the IDMC reviews has reviewed all safety data up to 30 days after administration of Dose 2 (i.e., Day 61). The IDMC will review all accumulating safety data monthly throughout the period of vaccination and accumulating SAEs until the end of the second RSV transmission season.

Refer to Sections 9.10.2 and 9.10.3 of the protocol.

c Refer to Section 6.6.12.3 of the protocol

Table 1 Vaccines administered and vaccination schedules

Groups	Age* (Months) / (Visit, Day)				
	6-7 / (V1, D1)	7-8 / (V3, D31)	8-9 / (V5, D61)	10-11 / (V6, D121)**	14-18 / (V7)
1D RSV + Bexsero	1D RSV ChAd	FB	Bexsero	Bexsero	Bexsero
2D RSV + Bexsero	2D RSV ChAd	2D RSV ChAd	Bexsero	Bexsero	Bexsero
Bexsero	Bexsero	FB	Bexsero	FB	Bexsero
1D RSV + Nimenrix	1D RSV ChAd	FB	Nimenrix	Nimenrix	Nimenrix
2D RSV + Nimenrix	2D RSV ChAd	2D RSV ChAd	Nimenrix	Nimenrix	Nimenrix
Nimenrix	Nimenrix	FB	Nimenrix	FB	Nimenrix
1D RSV + Synflorix	1D RSV ChAd	FB	Synflorix	Synflorix	Synflorix
2D RSV + Synflorix	2D RSV ChAd	2D RSV ChAd	Synflorix	Synflorix	Synflorix
Synflorix	FB	Synflorix	Synflorix	FB	Synflorix
1D RSV + Menveo	1D RSV ChAd	FB	Menveo		Menveo
2D RSV + Menveo	2D RSV ChAd	2D RSV ChAd	Menveo		Menveo
Menveo	FB	Menveo	FB		Menveo
1D RSV + Placebo	1D RSV ChAd	FB			
2D RSV + Placebo	2D RSV ChAd	2D RSV ChAd			
Placebo	FB	FB			

V: Visit; D: Day; **1D**: 1 Dose (1.5×10^{10} vp/dose); **2D**: 2 Dose (5×10^{10} vp/dose); **RSV ChAd**: ChAd155-RSV vaccine; **FB**: Formulation buffer S9b.

* Assumes enrolled at 6 and 7 months of age for the vaccine Dose 1 to be administered before the first RSV season; the second dose will be given one month after the first dose. (RSV seasons will be determined for each country based on local epidemiological data [The RSV season is defined as the period of the year when 70% of the RSV cases have occurred in previous years. For the calculation, where available, data from up to the ten previous years should be applied. If the data permit calculation of the actual date of the beginning of the season, rather than approximation to the nearest month, this is desirable. Refer to the SPM for RSV seasons per country.])

** In countries where Menveo or Placebo is used as a comparator, no administration will be performed at Day 121 and therefore in those countries there will be no Visit 6 and it will be administered at the end of the first RSV season at Visit 7.

- Experimental design: Phase I/II, observer-blind, randomized, controlled, multi-centric study with three parallel groups
- Duration of the study: approximately 24 months.
 - Epoch 001: Screening Visit starting up to 30 days before first vaccination and ending on Day -1.
 - Epoch 002: primary starting at Visit 1 (Day 1) and ending at Visit 5 (Day 61).
 - Epoch 003: follow-up starting after Visit 5 (Day 61)* and ending at Visit 7 (end of the first RSV transmission season).
 - Epoch 004: follow-up starting after Visit 7 (end of the first RSV transmission season)* and ending at Visit 8 (end of the second RSV transmission season).

*Any safety, immunogenicity and disease surveillance data collected beyond Visit 5 (Day 61) will be collected in Epoch 003. Any safety, immunogenicity and disease surveillance data collected beyond Visit 7 (end of the first RSV transmission season) will be collected in Epoch 004. Refer to the SPM for RSV transmission seasons per country.

- Primary Completion Date (PCD): Visit 5 (Day 61).

- End of Study (EoS): Last testing results released of samples collected at Visit 8 (end of the second RSV transmission season) related to primary and secondary endpoints.*

* Up to Visit 8 (end of the second RSV season), there will be monthly nasal swab to detect asymptomatic RSV infections during the RSV season *or* if following active or a passive surveillance contacts, a subject presents symptoms of respiratory tract infection (RTI), a nasal swab will be collected.

- Study groups:

Table 2 Study groups and epochs foreseen in the study

Study groups	Target Number of subjects	Age (Min/Max)	Epochs			
			Epoch 001	Epoch 002	Epoch 003	Epoch 004
1D RSV + Bexsero	50	6 – 7 months	N/A	x	x	x
1D RSV + Nimenrix		6 – 7 months	N/A	x	x	x
1D RSV + Synflorix		6 – 7 months	N/A	x	x	x
1D RSV + Menveo		6 – 7 months	N/A	x	x	x
1D RSV + Placebo		6 – 7 months	N/A	x	x	x
2D RSV + Bexsero	50	6 – 7 months	N/A	x	x	x
2D RSV + Nimenrix		6 – 7 months	N/A	x	x	x
2D RSV + Synflorix		6 – 7 months	N/A	x	x	x
2D RSV + Menveo		6 – 7 months	N/A	x	x	x
2D RSV + Placebo		6 – 7 months	N/A	x	x	x
Bexsero	50	6 – 7 months	N/A	x	x	x
Nimenrix		6 – 7 months	N/A	x	x	x
Synflorix		6 – 7 months	N/A	x	x	x
Menveo		6 – 7 months	N/A	x	x	x
Placebo		6 – 7 months	N/A	x	x	x

1D: 1 Dose (1.5×10^{10} vp/dose); **RSV:** ChAd155-RSV vaccine; **2D:** 2 Dose (5×10^{10} vp/dose); **N/A:** Not Applicable.

Table 3 Study groups and treatment foreseen in the study

Treatment name	1D RSV ChAd	2D RSV ChAd	Bexsero	Nimenrix	Synflorix	Menveo	FB
Vaccine/ Product name	1D ChAd155-RSV 1.5X10 ¹⁰ vp/dose	2D ChAd155-RSV 5X10 ¹⁰ vp/dose	Bexsero	Nimenrix	Synflorix	Menveo	FB
Study Groups							
1D RSV + Bexsero	x		x				x
1D RSV + Nimenrix	x			x			x
1D RSV + Synflorix	x				x		x
1D RSV + Menveo	x					x	x
1D RSV + Placebo	x						x
2D RSV + Bexsero		x	x				
2D RSV + Nimenrix		x		x			
2D RSV + Synflorix		x			x		
2D RSV + Menveo		x				x	
2D RSV + Placebo		x					
Bexsero			x				x
Nimenrix				x			x
Synflorix					x		x
Menveo						x	x
Placebo							x

ChAd155-RSV: Chimpanzee Adenovirus Type 155 RSV vaccine; **FB:** Formulation buffer S9b; **RSV ChAd:** ChAd155-RSV vaccine; **1D:** 1 Dose (1.5x10¹⁰ vp/dose); **2D:** 2 Dose (5x10¹⁰ vp/dose).

- Controls: active comparator vaccines (*Bexsero*, or *Nimenrix*, or *Synflorix*, or *Menveo*, or Placebo (FB)*).
 - * The choice of active comparator vaccine (*Bexsero*, *Nimenrix*, *Synflorix*, or *Menveo*) or Placebo is done at the country level. Refer to the ICF for the local choice of comparator/Placebo.
- Vaccination schedules:
 - **RSV investigational vaccine:** In the 1 Dose (1D) groups, a single lower dose of 1.5x10¹⁰ vp will be administered IM at Day 1 (Visit 1). Formulation buffer will be administered in the 1D groups at Day 31 (Visit 3). In the 2 Dose (2D) groups, two doses of 5x10¹⁰ vp will be administered IM according to a 0, 1-month schedule, (i.e., at Day 1 [Visit 1] and Day 31 [Visit 3]) (see Figure 1 and Table 1). Dose 1 will be administered before the first RSV season and the second dose will be given one month after the first dose (RSV seasons will be determined for each country based on local epidemiological data and documented in the Study Procedures Manual [SPM]. The RSV season is defined as the period of the year when 70% of the RSV cases have occurred in previous years. For the calculation, where available, data from up to the ten previous years should be applied. If the data permit calculation of the actual date of the beginning of the season, rather than approximation to the nearest month, this is desirable.)
 - **Comparator or Placebo:** In countries where *Bexsero* or *Nimenrix* is used as a control, two doses will be administered IM with at least a 2-month interval between these primary doses. A booster dose will be administered IM in the second year of life at Visit 7, with an interval of at least 2 months between the

primary series and booster dose. The first *Bexsero* or *Nimenrix* dose will be administered at Day 1 (Visit 1) (in the groups receiving only *Bexsero* or *Nimenrix*, respectively). In the groups receiving only *Bexsero* or *Nimenrix*, the second dose will be at Day 61 (Visit 5). The first *Bexsero* or *Nimenrix* dose to be administered to the 1D and 2D RSV groups will be at Day 61 (Visit 5), following the 1 or 2 RSV vaccine doses, respectively. The second dose of *Bexsero* or *Nimenrix* in the 1D and 2D groups will be at Day 121 (Visit 6). Formulation buffer will be administered, when neither RSV vaccine nor comparator is scheduled, at the 5 vaccination visits (see Figure 1 and Table 1).

- In countries where *Synflorix* is used as a control, two doses will be administered IM with at least a 1 month interval between these primary doses. A booster dose will be administered IM in the second year of life at Visit 7. The first *Synflorix* dose will be administered at Day 31 (Visit 3) (in the group receiving only *Synflorix*). In the group receiving only *Synflorix*, the second dose will be at Day 61 (Visit 5). The first *Synflorix* dose to be administered to the 1D and 2D RSV groups will be at Day 61 (Visit 5), following the 1 or 2 RSV vaccine doses, respectively. The second dose of *Synflorix* in the 1D and 2D groups will be at Day 121 (Visit 6). Formulation buffer will be administered, when neither RSV vaccine nor comparator is scheduled, at the 5 vaccination visits (see Figure 1 and Table 1).
- In countries where *Menveo* is used as a control, two doses will be administered IM at least 3 months apart with the second dose in the second year of life at Visit 7. The first *Menveo* dose will be administered at Day 31 (Visit 3) (in the group receiving only *Menveo*). The first *Menveo* dose to be administered to the 1D and 2D RSV groups will be at Day 61 (Visit 5), following the 1 or 2 RSV vaccine doses, respectively. Since the second *Menveo* dose has to be administered in the second year of life at Visit 7, no administration will be performed at Day 121 (Visit 6). Formulation buffer will be administered, when neither RSV vaccine or comparator is scheduled, at the 4 vaccination visits (see Figure 1 and Table 1).
- In countries where Placebo is used as a control, one dose will be administered IM at Day 31 (Visit 3) in the 1D RSV + Placebo group and two IM doses will be administered IM according to a 0, 1-month schedule at Day 1 (Visit 1) and Day 31 (Visit 3) in the Placebo group (see Figure 1 and Table 1).
- Treatment allocation: infants will be randomized using a centralized randomization system on internet (SBIR) before first vaccination and after assessment of eligibility (i.e., after screening conclusion) (refer to Section 6.2.2 of the protocol for details about randomization of treatment). The randomization algorithm will use a minimization procedure accounting for country as a minimization factor and the grouping comparator/placebo as a stratification factor.
- Blinding: not applicable for Epoch 001 (Screening Visit), observer-blind in Epoch 002 and single-blind in Epoch 003 and Epoch 004. Refer to Section 6.3 of the protocol for details of blinding procedure.

- Blinding of study epochs

Study Epochs	Blinding
Epoch 001	N/A
Epoch 002	observer-blind
Epoch 003	single-blind
Epoch 004	single-blind

- Sampling schedule:

- Blood samples for **hematology/biochemistry** will be taken from all infants at Screening (up to 30 days before first vaccination to Day -1). Blood samples for **hematology/biochemistry** may be taken from infants at any timepoints, if deemed necessary by the investigator. Refer to Table 12 of the protocol for the list of parameters to be tested.
- Refer to Section 6.6.1.2.2 and Figure 2 of the protocol for information about the re-testing of samples in case of any Grade 1 abnormality with potential clinical relevance (according to investigators judgment) or any \geq Grade 2 abnormality.
- Blood samples for **humoral immunogenicity** will be taken from all subjects at Screening and on Day 31, Day 61, and at the visit occurring at the end of the first RSV transmission season.
- Blood sample for **assessment of mechanism of illness (potential ERD)** will be taken from subjects hospitalized for LRTI (only for RSV-positive subjects using a locally available RSV test).
- Nasal swab: there will be monthly nasal swab to detect asymptomatic RSV infections during the RSV season and if following active or a passive surveillance contacts, a subject present symptoms of RTI, a nasal swab will be collected (as well as a sample for local testing i.e., the type of sample to be determined locally [e.g., swab, etc.]) (Refer to the SPM).
- Study visits: Other than the screening visit and assessment visits for active/passive surveillance, there will be 8 study visits except in countries where *Menveo* or Placebo is used as a control where there will be 7 study visits.
 - In countries where *Menveo* is used as a comparator, no administration will be performed at Day 121 and therefore in those countries there will be no Visit 6 and it will be administered at the end of the first RSV season at Visit 7 (refer to Table 2 and 7 of the protocol).
 - In countries where Placebo is used as a control, no vaccine administration will be performed after Visit 3 and therefore in those countries there will be no Visit 6. There will be a Visit 5 and Visit 7 for countries using Placebo and all other study procedures will occur at these visits except vaccination.
 - Visit 2 (Day 8), Visit 4 (Day 38), and Visit 8 (no blood sampling for immune response and no vaccine administration) may take place in the subject's home or at the investigators clinical facility as appropriate to the circumstances in the judgment of the investigator.

- For authorized sites only, Visit 5 (Day 61) and Visit 7 (both with blood sampling) may also take place in the subject's home or at the investigators clinical facility as appropriate to the circumstances in the judgment of the investigator.
- Data collection: electronic Case Report Form (eCRF).
- Safety monitoring: internal safety review committee (iSRC) and IDMC (refer to Section 9.10 of the protocol).
- **Surveillance for RSV-RTI, difficulty in breathing, and wheezing episodes**
Surveillance period will be carried out from Visit 1 (after Dose 1) until the last study visit (end of the second RSV transmission season). In order to detect asymptomatic RSV-RTI, monthly nasal swabs for analysis at sponsor laboratory will be performed for all subjects during the RSV season. In order to timely detect RSV-RTI and to ensure cases are timely captured by the study sites, both active and passive surveillance will be conducted:
 - **Passive surveillance:** parent(s)/LAR(s) are instructed to contact the investigator/study staff as soon as the subject experiences new RTI symptoms (cough, runny nose or blocked nose) or worsening of RTI symptoms, or in case of difficulty in breathing or wheezing.
 - **Active surveillance:** parent(s)/LAR(s) of all the subjects will be contacted by the investigator/study staff on a regular basis (weekly during the RSV season and every month outside the RSV season) to identify any potential RSV-RTI and to remind the parent(s)/LAR(s) of the subjects to report any new occurrence of RTI symptoms (cough, runny nose or blocked nose), or in case of difficulty in breathing or wheezing as soon as possible.

Refer to Section 9.2 of the protocol for more information about active and passive surveillance.

- Surveillance for spontaneous or excessive bleeding - Subjects' parent(s)/LAR(s) will be instructed to contact the investigator/study staff if their child presents symptoms of spontaneous bleeding or easy bruising or if their child develops a rash, within 30 days after either vaccination (Visit 1 and Visit 3), in order to detect any thrombocytopenic petechiae or purpura. The investigator will, based on his/her medical judgment, measure the total blood count and appropriately investigate infants with clinical suspicion of low platelets.
- **Group description:** - For the blinded report on safety/reactogenicity, the analyses will be presented as one group (RSV groups and Placebo group being pooled).

The following group names for the unblinded analysis will be used in the TFLs, to be in line with the T-domains:

Group order in tables	Group label in tables	Group definition for footnote	Pooled Groups label in tables – UNBLINDED ANALYSIS	Pooled definition for footnote - UNBLINDED ANALYSIS
1	RSVBEX1D	RSV 1D + BEXERO 3D	RSV 1D	Pooled 1D RSV
2	RSVNIM1D	RSV 1D +NIMENRIX 3D		
3	RSVSYN1D	RSV 1D +SYNFLORIX 3D		
4	RSVMEN1D	RSV 1D +MENVEO 2D		
5	RSVPBO1D	RSV 1D + PLACEBO		
6	RSVBEX2D	RSV 2D + BEXERO 3D	RSV 2D	Pooled 2D RSV
7	RSVNIM2D	RSV 2D +NIMENRIX 3D		
8	RSVSYN2D	RSV 2D +SYNFLORIX 3D		
9	RSVMEN2D	RSV 2D +MENVEO 2D		
10	RSVPBO2D	RSV 2D + PLACEBO		
11	BEXERO	BEXERO 3D	COMP_PLB	Pooled comparator
12	NIMENRIX	NIMENRIX 3D		
13	SYNFLORIX	SYNFLORIX 3D		
14	MENVEO	MENVEO 2D		
15	PLACEBO	PLACEBO		

3. OBJECTIVES/ENDPOINTS

3.1. Objectives

3.1.1. Primary Objective

- To evaluate the safety and reactogenicity of the RSV investigational vaccine when administered IM as one (1.5×10^{10} vp) dose or as two (5×10^{10} vp) doses according to a 0, 1-month schedule, up to 60 days after Dose 1 (i.e., Day 61) in infants aged 6 and 7 months.

3.1.2. Secondary Objective

- To evaluate the occurrence of RSV respiratory tract infections of any severity from Visit 1 (Day 1, after Dose 1) up to the end of the first RSV transmission season, in infants aged 6 and 7 months
- To evaluate the safety of the RSV investigational vaccine when administered IM as one (1.5×10^{10} vp) dose or as two (5×10^{10} vp) doses according to a 0, 1-month schedule, from study start (Day 1) up to the end of the second RSV transmission season in infants aged 6 and 7 months
- To evaluate the occurrence of RSV respiratory tract infections from Visit 1 (Day 1, after Dose 1) up to the end of the second RSV transmission season, in infants aged 6 and 7 months.

- To evaluate the occurrence of very severe RSV-LRTI from Visit 1 (Day 1, after Dose 1) up to the end of the first RSV transmission season in RSV infected infants aged 6 and 7 months with a negative RSV exposure status (at screening based on in-stream baseline serological testing).
- To evaluate the humoral immunogenicity induced by the RSV investigational vaccine when administered IM as one (1.5×10^{10} vp) dose or as two (5×10^{10} vp) doses according to a 0, 1-month schedule, from study start (Day 1) up to the end of the first RSV transmission season, in infants aged 6 and 7 months.

3.1.3. Tertiary objective

- If deemed necessary, to further characterize the immune response of the RSV investigational vaccine when one (1.5×10^{10} vp) dose or two (5×10^{10} vp) doses are administered IM according to a 0, 1-month schedule to infants aged 6 and 7 months

3.2. Endpoints

3.2.1. Primary endpoints

- Occurrence of adverse events (AEs) from first vaccination (Day 1) up to Day 61
 - Occurrence of each solicited local and general AE, during a 7-day follow-up period after each vaccination (i.e., the day of vaccination and 6 subsequent days)
 - Occurrence of any unsolicited AE, during a 30-day follow-up period after each vaccination (i.e., the day of vaccination and 29 subsequent days)
 - Occurrence of any serious adverse event (SAE) from Day 1 up to Day 61
 - Occurrence of episode of spontaneous or excessive bleeding (AE of special interest), during a 30-day follow-up period after each vaccination

3.2.2. Secondary endpoints

- Occurrence of RSV-RTI, RSV-LRTI, severe RSV-LRTI and very severe RSV-LRTI (according to standardized case definitions) as from first vaccination (Day 1) up to the end of the first RSV transmission seasons.
- Occurrence of RSV-RTI, RSV-LRTI, severe RSV-LRTI and very severe RSV-LRTI (according to standardized case definitions) as from first vaccination (Day 1) up to the end of the second RSV transmission seasons.
- Occurrence of SAEs from first vaccination (Day 1) up to the end of the second RSV transmission seasons.
- Occurrence of RSV-LRTI (AE of special interest) as from first vaccination (Day 1) up to the end of the first RSV transmission season, and up to the end of the second RSV transmission seasons.

- Occurrence of very severe RSV-LRTI (according to standardized case definitions) among RSV infected infants with a negative RSV exposure status (at screening based on in-stream baseline serological testing) from first vaccination (Day 1) up to the end of the first RSV transmission seasons.
- Humoral response to the investigational RSV vaccine, pre-vaccination (Screening), post-Dose 1 (Day 31) and post-Dose 2 (Day 61 and at the end of the first RSV transmission season):
 - Neutralizing antibody titers against RSV-A
 - RSV F antibody concentrations

3.2.3. Tertiary endpoints

- Humoral response to the investigational RSV vaccine, pre-vaccination (Screening), post-Dose 1 (Day 31) and post-Dose 2 (Day 61)
 - Palivizumab-competing antibody concentrations
- Any further exploratory immunology to detect disease-related or vaccine-related immune responses, such as but not limited to
 - Anti-vector immunity: neutralization

4. ANALYSIS SETS

4.1. Definition

4.1.1. Exposed Set

The Exposed Set (ES) will include all subjects with at least one study vaccine administration documented.

- A safety analysis based on the ES will include all vaccinated subjects.
- An immunogenicity analysis will be conducted on the ES and will include all vaccinated subjects for whom immunogenicity data are available.

The ES analysis will be performed per treatment actually administered at Dose 1

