4.2.1. Elimination from Exposed Set (ES)

Code 1030 (Study vaccine not administered at all), code 900 (invalid informed consent) and code 800 (fraudulent data) will be used for identifying subjects eliminated from ES.

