4.2.3. Elimination from Per-protocol analysis Set (PPS)

4.2.3.1. Excluded subjects

A subject will be excluded from the PPS analysis under the following conditions

For codes 1040, 1070, 1080, 1090, 2040, 2060, 2070, 2080: subjects will be eliminated from a specific visit (at which the condition is met) onwards.

For codes 2090, 2100, 2120: subjects will be eliminated at the specific visit at which the condition is met

Code	Condition under which the code is used	Visit (timepoints) where the code is applicable	Applicable for analysis set
800	Fraudulent data	All	All
900	Invalid informed consent	All	all
1030	Study vaccine not administered at all	All	Safety, immunology
1040	Administration of concomitant vaccine(s) forbidden in the protocol:- 
 • Any investigational or non-registered product (drug or vaccine) other than the study vaccines used during the study period • A vaccine not foreseen by the study protocol administered during the period starting 30 days before the first dose and ending 30 days after the last dose of vaccine*, with the exception of: 
 – Scheduled routine pediatric vaccines which may be administered \geq 7 days before a dose and \geq 7 days after a dose of study vaccines, with the exception of live viral vaccines which may be administered 	Visit 3,5, 7	Immunogenicity

Code	Condition under which the code is used	Visit (timepoints) where the code is applicable	Applicable for analysis set
	≥ 14 days before a dose or ≥ 7 days after a dose. – Vaccines needed for urgent individual medical need (e.g., rabies prophylaxis)		
1050	Randomisation failure	All	Immunogenicity
1060	Randomisation code was broken	All	Immunogenicity
1070	Subjects got vaccinated with the correct vaccine but containing a lower volume	All	Immunogenicity
1070	Vaccination not according to protocol: 
Wrong replacement or study vaccine administered (not compatible with the vaccine regimen associated to the treatment number)Site or route of study vaccine administration wrong or unknownAdministration not according to protocol for reason specified by the investigator, other than side, site and route	All	Immunogenicity
1080	Vaccine temperature deviation (vaccine administered despite a Good Manufacturing Practices (GMP) no-go temperature deviation for RSV vaccines only)	All	Immunogenicity
1090	Expired vaccine administered (only applicable for RSV vaccine)	All	Immunogenicity

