5.3. Analysis of safety and reactogenicity

5.3.1. Analysis of safety and reactogenicity planned in the protocol

5.3.1.1. Within groups assessment

The safety will be descriptively summarized based on the ES. The analysis of local AEs, general AEs and fever will be reported for each RSV + comparator vaccine group and each active control comparator group and also for the pooled RSV vaccine and pooled comparator groups. For the analysis of SAEs and AE of specific interest, the analysis will be performed only on the pooled RSV and pooled comparator groups.

The percentage of subjects with at least one local AE (solicited and unsolicited), with at least one general AE (solicited and unsolicited) and with any AE during the 7-day or 30-day follow-up period will be tabulated with exact 95% confidence interval (CI) after each vaccine dose and overall. The percentage of doses followed by at least one local AE (solicited and unsolicited), by at least one general AE (solicited and unsolicited) and by any AE during the 7-day or 30-day follow-up period will be tabulated, overall vaccination course, with exact 95% CI. The same computations will be done for Grade 3 AEs, for any AEs considered related to vaccination for any Grade 3 AEs considered related to vaccination and AEs resulting in a medically attended visit.

The percentage of subjects reporting each individual solicited local AE (any grade, Grade 2, Grade 3, resulting in a medically attended visit) and solicited general AE (any grade, Grade 2, Grade 3, any related, Grade 2 related, Grade 3 related, resulting in medically attended visit) during the 7-day follow-up period (Day 1-7) will be tabulated for each

RSV + comparator vaccine group and each active control comparator group and also for the pooled RSV vaccine and pooled comparator groups after each vaccine dose and overall. Similarly, the percentage of doses followed by each individual solicited local and general AE and their sub-categories, will be tabulated, overall vaccination course, with exact 95% CI.

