5.3.2.3. Solicited Adverse Events

All analyses will be based on the ‘as treated’ analysis set. Solicited adverse events will be reported daily during the 7-day (from Day 1 to Day 7) follow up period after each vaccination, using structured diaries.

In order to summarize the data, the maximum intensity of local injection site redness/swelling (in mm) and fever (in $^{\circ}\text{C}$) will be categorized as follows:

Grading	Redness/swelling	Fever
0:	None	$< 38.0^{\circ}\text{C}$ (100.4°F)
1:	< 5 mm	$\geq 38.0^{\circ}\text{C}$ (100.4°F) - $\leq 39.0^{\circ}\text{C}$ (102.2°F)
2:	$> 5 - \leq 20$ mm	$> 39.0^{\circ}\text{C}$ (102.2°F) - $\leq 40.0^{\circ}\text{C}$ (104.0°F)
3:	> 20 mm	$> 40.0^{\circ}\text{C}$ (104.0°F)

Fever is defined as temperature $\geq 38.0^{\circ}\text{C} / 100.4^{\circ}\text{F}$ (regardless of the location of measurement). The preferred location for measuring temperature in this study will be the oral cavity. Body temperature will also be summarized by 0.5°C increments as follows: $\geq 38.0, >38.5, >39.0, >39.5, >40.0^{\circ}\text{C}$.

For each of the time points or time intervals presented in the summaries, only subjects with at least one plausible observation (i.e., any non-missing values but excluding “Not done/unknown” and implausible values) for the solicited adverse events in the interval of interest will be considered. Subjects without plausible data (i.e. missing values or reported as “Not done/unknown” and implausible values) will be removed from the denominator to prevent a downward bias (towards zero).

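### Safety groups are fixed by the Dose 1 product, so an infant given RSV vaccine in error at Visit 3 after comparator or buffer at Visit 1 would still be counted as a control

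*SAP*

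**What the plan says.** Section 4.1.1 of the SAP defines the Exposed Set (ES) and gives its only grouping rule: "The ES analysis will be performed per treatment actually administered at Dose 1". On membership it adds: "A safety analysis based on the ES will include all vaccinated subjects".

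Section 5.3.1.1 places safety on this set: "The safety will be descriptively summarized based on the ES". Section 5.4.1 uses the ES, and its subset with negative RSV exposure status at screening, for RSV infection, RTI and LRTI, including relative risks against the pooled control.

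Table 1 in Section 2 shows that the RSV regimens cover two visits. RSV 1D infants receive RSV vaccine at Visit 1 and buffer at Visit 3, RSV 2D infants receive RSV vaccine at both, and controls receive comparator or buffer at both.

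For removal from the ES, Section 4.2.1 says: "Code 1030 (Study vaccine not administered at all), code 900 (invalid informed consent) and code 800 (fraudulent data) will be used". A wrong product falls under code 1070 in Section 4.2.3.1, "Wrong replacement or study vaccine administered (not compatible with the vaccine regimen associated to the treatment number", and that code applies to immunogenicity only.

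For solicited events, Section 5.3.2.3 says: "All analyses will be based on the ‘as treated’ analysis set". Section 4 defines no set of that name.

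**The concern.** A rule that looks only at Visit 1 cannot register a wrong product at Visit 3. Three errors are possible:

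- A control given RSV vaccine at Visit 3 stays in COMP_PLB.
- An RSV 1D infant given RSV vaccine instead of buffer stays in RSV 1D.
- An RSV 2D infant given buffer stays in RSV 2D.

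The first matters most. Safety is the primary objective, and Section 5.3.1.2 subtracts COMP_PLB from each RSV group. If the vaccine causes reactions or worse RSV disease, a vaccinated infant counted as a control adds those events to the reference rate and shrinks the apparent harm. An RSV 2D infant given buffer dilutes the RSV 2D rate in the same direction. An RSV 1D infant given extra vaccine would raise the RSV 1D rate instead, so that error mainly blurs the contrast between the two regimens.

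The SAP foresees a wrong product: it has a code for it and protects the immunogenicity set. It has no matching rule for safety.

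**Working it through.** No figure in the SAP depends on this rule, so there is nothing to reproduce. The check has two parts.

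**1. Does any other rule correct the group?** Take a control infant given buffer at Visit 1 and RSV vaccine in error at Visit 3.

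| SAP section | Effect on this infant |
|---|---|
| 4.1.1 | Group follows the Dose 1 product, so COMP_PLB |
| 4.2.1 | Not removed; none of codes 1030, 900 and 800 applies |
| 4.2.3.1, code 1070 | Removed from the immunogenicity per-protocol set only |
| 10.1.1 | Events are linked to the most recent dose; the group is unchanged |
| 5.3.2.3 | Names an 'as treated' set, but the only definition of treatment received is the Dose 1 rule |

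The infant stays in COMP_PLB. In Templates 16 and 18, which tabulate solicited events after the Visit 3 vaccination by group, a reaction to RSV vaccine would appear under the control.

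**2. How large could the effect be?** Inputs: a target of 50 per pooled group (Table 2), Clopper-Pearson intervals for proportions (Section 10.1.3.20) and Miettinen-Nurminen intervals for differences (Section 10.1.3.21), all at 95%. The event counts and numbers of errors are assumptions.

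*One infant.* One infant is 1/50 = 2.0 points.

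- 0/50: upper limit 1 − 0.025^(1/50) = 7.1%.
- 1/50 = 2.0%: interval 0.05% to 10.6%.

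*A contrast.* Assume 5/50 with the event in an RSV group and 2/50 in the control before any error: difference 10.0 − 4.0 = 6.0 points (−4.9 to 18.0), RR = 5/2 = 2.50. Now let k further control infants have received RSV vaccine in error at Visit 3, each with the event. The Dose 1 rule compares 5/50 with (2 + k)/50. Grouping by any RSV vaccine received compares (5 + k)/(50 + k) with 2/(50 − k).

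| k | Dose 1 rule: difference (95% CI) | RR | By RSV vaccine received: difference (95% CI) | RR |
|---|---|---|---|---|
| 1 | 4.0 (−7.7 to 16.3) | 1.67 | 7.7 (−3.6 to 20.0) | 2.88 |
| 2 | 2.0 (−10.4 to 14.7) | 1.25 | 9.3 (−2.4 to 21.9) | 3.23 |
| 3 | 0.0 (−12.9 to 12.9) | 1.00 | 10.8 (−1.2 to 23.6) | 3.55 |

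For k = 1, if the infant is taken out of COMP_PLB and reported separately, the comparison is 5/50 with 2/49, and RR = 0.100/0.0408 = 2.45.

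The right-hand columns exceed 2.50 because every misdosed infant is assumed to have the event; they are not estimates of a true effect. The case k = 3 means 3/50 = 6% of controls misdosed, all with events, and is extreme. With k = 0 the two rules agree.

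**The case against.** The strongest case for the present rule is that it is clear and works for the usual situations. The three pooled groups already differ at Visit 1, so an error at Visit 1 is classified correctly. Events are counted from first vaccination, so grouping at Dose 1 fixes the group when follow-up starts. It also keeps in RSV 2D an infant who reacts to the first dose and never receives the second. Safety is descriptive, and Section 6 calls comparative analyses exploratory. These points stand. They are why the rule should remain the default and why the point is of moderate weight.

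Three stronger readings are tempting, and the SAP does not support them.

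- *The rule cannot tell the individual control groups apart.* Table 1 gives buffer at Day 1 to Synflorix controls ("Synflorix FB Synflorix Synflorix FB Synflorix"), and also to Menveo and Placebo controls. But Section 2 has the comparator chosen at country level, with country as a minimization factor and the comparator/placebo grouping as a stratification factor. Within a country, Dose 1 separates the three arms.
- *Wrong second doses are ignored altogether.* They are not. Code 1070 acts on immunogenicity, Section 5.1.2 and Template 4 summarize deviations leading to elimination, with an individual listing, and SAEs are described in detail and listed by subject (Section 5.3.1.1, Template 23). A serious event in a misdosed infant could be traced. It would still be counted in the wrong group.
- *Results should also be shown without every infant whose sequence matches no planned regimen.* That could remove RSV 2D infants who stopped because of a Dose 1 reaction, a selection on a post-vaccination event. Templates 8 and 26 foresee completion with one dose and treatment discontinuation for adverse events.

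**Conclusion.** The point holds as a gap in the grouping rule for one foreseeable error. In the safety and RSV disease analyses, a known RSV vaccine recipient can be counted as a control, and a wrong Visit 3 product in RSV 1D or RSV 2D leaves the group unchanged. The undefined 'as treated' wording does not resolve this.

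At 50 per group, each misplaced control with an event moves the control rate by 2 points. In the assumed 5/50 versus 2/50 example, one such infant gives an RR of 1.67, against 2.45 if reported separately or 2.88 if counted with the RSV group. The bias toward no harm requires both a Visit 3 error in a control and an event that the vaccine made more likely. The SAP gives no error rate, so the expected size is unknown and may be zero. A reader should not infer that the trial's safety results are biased, only that the rule would misclassify if such an error occurred.

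**What to change.** Keep Dose 1 grouping as the default for the ES, including for infants who simply miss the second dose. Then add to Section 4.1.1:

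1. For safety and RSV disease analyses, an infant with any documented RSV vaccine administration is not counted in COMP_PLB for events after that administration. Earlier events stay with the product given at Visit 1. State how the infant enters the denominators of tables that run from Dose 1 onward.
2. All infants given a wrong product at Visit 3 are listed, with planned and received products.
3. A sensitivity analysis groups infants by RSV vaccine actually received: none, 1D regimen, 2D regimen, other.

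In Section 5.3.2.3, replace or define the 'as treated' set so that it matches this rule.

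The cost is a few sentences, one extra derivation, and a group label that may change at Visit 3 for a few infants. It should be settled before the Day 61 analysis, when Section 7.1 unblinds the statistician, so that no regrouping is decided with treatment assignments known.
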